| HSCT | Hematopoietic stem cell transplant |
| HRQL | Health-related quality of life |
| AE | Adverse event |
| EHR | Electronic Health Record |
| MRN | Medical Record Number |

ABSTRACT

Context: Patients undergoing treatment for cancer face disease, treatment, and environmental obstacles to sufficient, sound sleep¹. Hospitalizations can further worsen sleep quality and quantity due to overnight vitals checks, medication administration, blood draws, and environmental noise and light². For patients undergoing hematopoietic stem cell transplant (HSCT), the risk for poor sleep is especially high due to protracted hospitalization, frequent vitals checks resulting in multiple night awakenings³, and high symptom burden peaking approximately 10 days post-transplant⁴.

Objectives:

Primary: Test the acceptability and feasibility of protecting one 6-hour window for nighttime sleep (intervention) relative to regular vitals checks (observation only periods) during HSCT recovery.

Secondary: Assess the effect of one 6-hour window for nighttime sleep on subject sleep and engagement in supportive care on the HSCT unit.

Study Design:

Aggregated N=1 randomized controlled design. All participants will undergo a 5 day observation and then be randomized to receive the 5 day intervention (extended vitals checks) during either nights of days +5-+9 or days +10-+14.

Setting/Participants:

Inpatients on the HSCT Unit at CHOP

Study Interventions and Measures:

[figure not shown]
Intervention—increasing time between vitals checks from every 4 hours to one 6-hour period at night.

Subjects will wear an actigraph for the duration of the study, complete a daily sleep diary, and complete self- and parent-proxy psychosocial measures (symptom burden, health related quality of life, sleep) and acceptability. Medical record review will also be conducted to assess vitals check frequency.

TABLE 1: SCHEDULE OF STUDY PROCEDURES

| Visit | Purpose | Main Procedures | Duration |
|--------------------------------|--------------------------|--|------------|
| Visit 1 Pre-transplant | Baseline measures | Complete Informed consent Complete CEFIS Complete self-report measures Give actigraph | 35 minutes |
| Visit 2, Transplant Day 0 | Start actigraph | Review actigraphy procedures | 5 minutes |
| Visit 3, Transplant Day +5 | Randomization | Randomize to intervention start Complete self-report measures | 20 minutes |
| Visit 4, Transplant Day +10 | Psychosocial measures | Complete self-report measures | 15 minutes |
| Visit 5, Transplant Day +15 | End of Study | Return actigraph, Complete self-report measures including acceptability measure | 20 minutes |

.

FIGURE 1: STUDY DIAGRAM

*Each study period will include nights and symptom burden and sleep will be collected the day following the end of the study period. For example, sleep from night +4 and symptom burden for the day 0-+4 period will be collected on day +5.

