1 BACKGROUND INFORMATION AND RATIONALE

1.1 Introduction

Patients undergoing treatment for cancer face disease, treatment, and environmental obstacles to sufficient, sound sleep¹. Hospitalizations can further worsen sleep quality and quantity due to overnight vitals checks, medication administration, blood draws, and environmental noise and light². For patients undergoing HSCT, the risk of poor sleep is especially high due to protracted hospitalization, frequent vitals checks resulting in multiple night awakenings³, and high symptom burden peaking approximately 10 days post-transplant⁴. Sleep quality and quantity is associated with immune functioning⁵, wound healing⁶, and resistance to infection⁷, all critical to physical recovery from cancer and cancer treatments. Poor sleep may also have a psychosocial impact by limiting engagement in supportive care (PT/OT/School/Creative Arts Therapy/Psychology) due to compensatory daytime sleep and fatigue⁸. Together the physical impact of poor sleep and limited engagement in supportive care may hinder HSCT recovery. Frequent vitals checks are one potential intervention target when seeking to improve sleep. Vitals checks every 4 hours are necessary during conditioning and immediately post-transplant, but for many patients extending the time between vitals checks is possible. Through an aggregated N=1 randomized controlled design (each patient will serve as their own control, with the timing of the 5-day intervention period determined by randomization), the current study will test acceptability, feasibility, and impact on sleep and supportive care engagement of protecting one 6-hour window for nighttime sleep (intervention) relative to regular vitals checks (observation) during HSCT recovery.

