2.1 Primary Objective (or Aim)

The primary aim of the study is to assess the feasibility and acceptability of increasing time between vitals checks in HSCT.

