5 STUDY EVALUATIONS AND MEASUREMENTS

5.1 Screening and Monitoring Evaluations and Measurements

5.1.1 Medical Record Review

Include a listing of the variables that will be abstracted from the medical chart (paper or electronic).

- Date of birth
- Date of diagnosis and treatment history
- Medications
- Length of hospitalization prior to starting the study
- Number of visits completed or declined with supportive services (physical therapy, occupational therapy, school, creative arts therapies, and/or psychology) for each study period (Days 0-+4 including nights, Days +5-+9 including nights, Days +10-+14 including nights).
- Frequency and timing of vitals checks for each day in the study.
- Medications used for supportive care for each study period (Days 0-+4 including nights, Days +5-+9 including nights, Days +10-+14).
- Transplant parameters including: type of transplant, disease status, cell processing, GVHD prophylaxis and infectionus prophylaxis.

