5.1.2 Other Evaluations, Measures

Subjects and caregivers will complete the following measures:

| Table 1. Study Measures. | | Baseline | Day +5 | Day +10 | Day +15 |
|--------------------------|--|----------|--------|---------|---------|
| Construct | Measure | | | | |
| Acceptability | Patient, caregiver, and nurse will respond to a brief questionnaire of acceptability of adjusting vitals checks. | | | | x |
| Demographics | Report of sex, race/ethnicity, age of child and caregiver | x | | | |
| COVID-19 Impact | COVID-19 Exposure and Family Impact Survey (CEFIS) to assess family exposure to and experience with COVID-19 through Yes/No responses (25 items); 12 items assessing the impact of the pandemic on | x | | | |

| | | | | | |
|---------------------------|---|---|---|---|---|
| | self/family with 1-4 intensity scale and 1 open-ended item | | | | |
| HRQL and related symptoms | Pediatric Quality of Life Inventory—Stem Cell Transplant Module. This measure assesses HRQL and symptoms relevant to patients undergoing HSCT. The measure includes questions about pain, fatigue/sleep, nausea, communication, worry, nutrition, thinking and other symptoms answered on parallel child and adolescent with parent proxy forms (41 items). ²⁶ | x | x | x | x |
| Sleep | PROMIS Sleep Measures—Sleep disturbance, sleep-related impairment, and sleep hygiene over the past week-parallel parent/child forms (24 items) ²⁷ . | x | x | x | x |
| Supportive Care Use | EHR review to document engagement or refusal of PT/OT/School/Creative Art Therapy/ Psychology for each 5 day period. | | x | x | x |
| Actigraphy | Worn by participant day 0-night of Day +14, removing on awakening on Day+15. To validate actigraphy: bedtime, waketime, night awakenings, naps, time actigraph was off reported daily through text messages delivered via REDCap and its integration with Twilio. | | | | |

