6 STATISTICAL CONSIDERATIONS

6.1 Primary Endpoint

The primary endpoint is the acceptability and feasibility of the intervention. Acceptability will be measured by subjects, caregivers, and nursing ratings of the intervention. Feasibility will be measured through study staff documented medical eligibility to participate in the intervention each eligible day and by tracking compliance with extended vitals checks, through electronic health record (EHR) review.

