9.2 Data Collection and Management

Electronic health record data.

Investigators will generate a list of MRNs for participants with positive parental consent who have completed the survey. A trained research assistant with limited EHR access will extract treatment related data from the EHR. To obtain a password for the EHRs, all staff must complete training on the importance of patient privacy. Training on the Health Insurance Portability and Accountability Act (HIPAA) is required for all employees. With the EHRs, patient privacy is protected by multi-step, system wide processes. Anyone

wishing to view the charts of patients for whom they do not provide care must “break the glass.” This system requires a declaration of why the chart is being viewed and sends a message to both an employee’s supervisor and the hospital’s privacy officer. In summary, the inappropriate access to electronic health information is carefully monitored and strictly prohibited. All study files retained on CHOP’s secure network or within secure REDCap database will be accessed only by study staff using a CHOP issued, password-protected computer.

Child- and parent-report data:

Participants will complete daily sleep diary questions using REDCap and the integration with Twilio (a text messaging platform that integrates with REDCap). No PHI will be transmitted over text message. Electronic demographic, psychosocial, and acceptability surveys will also be obtained using REDCap. The CHOP Research Institute Center for Biomedical Informatics (CBMi) will be used as a central location for data processing and management. These data will be stored within REDCap by participant study ID.

Nurse acceptability data:

Nurses will complete acceptability questionnaires for each night they care for the child during the extended vitals check portion of the study using REDCap and the integration with Twilio (a text messaging platform that integrates with REDCap). No PHI will be transmitted over text message. The CHOP Research Institute Center for Biomedical Informatics (CBMi) will be used as a central location for data processing and management. These data will be stored within REDCap by participant study ID.

Confidentiality of On-Line Assessment.

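### The abstract and 1.1 state the primary objective as a comparison with regular vitals checks, but the endpoint and analysis describe the intervention only; a between-period summary of the overnight gap is available from planned data but not specified.

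*Combined protocol and SAP*

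**What the plan says.** **Objective.** The primary objective in the abstract is comparative and names the trial's own observation periods: "Test the acceptability and feasibility of protecting one 6-hour window for nighttime sleep (intervention) relative to regular vitals checks (observation only periods"). Section 1.1 says that each patient is their own control. It lists acceptability, feasibility, and impact on sleep and supportive care together, all for "protecting one 6-hour window for nighttime sleep (intervention) relative to regular vitals checks (observation) during HSCT recovery". Section 2.1 has no comparator: "The primary aim of the study is to assess the feasibility and acceptability of increasing time between vitals checks in HSCT".

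**Acceptability.** Section 6.1 says: "Acceptability will be measured by subjects, caregivers, and nursing ratings of the intervention". The measures table in 5.1.2 describes the instrument as "Patient, caregiver, and nurse will respond to a brief questionnaire of acceptability of adjusting vitals checks" and marks it at Day +15 only. For nursing staff, 9.2 says: "Nurses will complete acceptability questionnaires for each night they care for the child during the extended vitals check portion of the study".

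**Feasibility.** Section 6.1 says: "Feasibility will be measured through study staff documented medical eligibility to participate in the intervention each eligible day", together with compliance with extended checks taken from the health record. Section 6.3.2 summarises eligibility and delivery with descriptive statistics and specifies no contrast between periods.

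**Data collected.** The chart abstraction list in 5.1.1 includes "Frequency and timing of vitals checks for each day in the study".

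**The concern.** A reader of the abstract or 1.1 would expect the primary results to set extended checks against regular checks. Nothing in 6.1 or 6.3.2 does so, and 2.1 does not ask for it. The protocol therefore words its primary objective in two ways, and the comparative wording has no matching endpoint or analysis.

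More than wording is at stake on the feasibility side. Compliance on intervention nights shows that practice changed only if observation nights were different. The trial is unblinded (3.2), and 3.3.2 expects some nurses to care for several participants, so some carry-over of the new practice into observation nights is possible. In the other direction, a child who fails the daily eligibility check in 3.1.3 does not get the extended interval that night, which narrows the contrast. No planned summary would show either effect. If the sleep comparison in 6.2 and 6.3.2 then came out null, the report could not distinguish an intervention without effect from two conditions that were hardly different in practice.

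**Working it through.** The plan gives no alpha, power, effect size or success threshold for the primary endpoint, so there is no figure to reproduce. The check is to trace the objective through to the analysis.

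**Step 1. Is each part comparative?**

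| Element | Where | Comparator? |
|---|---|---|
| Primary objective | Abstract | Yes, observation periods |
| Statement of what the study tests | 1.1 | Yes, observation |
| Primary aim | 2.1 | No |
| Acceptability endpoint | 6.1 | No, ratings of the intervention |
| Acceptability instrument and timing | 5.1.2, 9.2 | None scheduled for an observation period |
| Feasibility endpoint | 6.1 | No, eligibility and compliance for extended checks |
| Primary analysis | 6.3.2 | No, descriptive |
| Sleep and supportive care (secondary) | 6.2, 6.3.2 | Yes, between periods |

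The secondary outcomes have a between-period contrast. The primary outcomes do not.

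**Step 2. What data will exist?** Section 3.1.3 sets three 5-day periods, ordered ABA or AAB (A observation, B intervention). Each child therefore has 2 × 5 = 10 observation nights and 1 × 5 = 5 intervention nights. Vitals times are abstracted on all 15.

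- With the 50 evaluable subjects of 3.3.2: 50 × 10 = 500 observation nights and 50 × 5 = 250 intervention nights.
- With the 16 subjects of 6.4: 16 × 10 = 160 and 16 × 5 = 80.

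(These two sample sizes disagree. That is a separate matter, and the present point does not depend on which is meant.)

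Scheduled acceptability ratings of an observation period: 0.

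**Step 3. What would the missing contrast change?** The documents give no rates, so these are assumptions for illustration. Suppose 85% of intervention nights contain a gap of at least 6 hours. The contrast is 85% minus the share of observation nights with such a gap:

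- observation share 0%: 85 − 0 = 85 points;
- observation share 25%: 85 − 25 = 60 points.

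The compliance figure in the report would be 85% in both cases.

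**Step 4. Is eligibility comparable across nights?** Section 3.1.3 says eligibility is assessed daily, but it describes provider confirmation only for intervention nights. It is unclear whether eligibility is recorded on observation nights. A contrast of eligible intervention nights with all observation nights could therefore be uneven. A contrast of all nights with all nights avoids this.

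**The case against.** **The comparator phrase may only define the intervention.** Section 1.2 uses nearly the same words as 1.1 purely to describe what is tested. The purpose in section 2, the aim in 2.1, the endpoint and the analysis are consistently non-comparative. In 1.1 the phrase closes a list that includes sleep and supportive care, where a comparison is planned. This reading is reasonable, and it is why aligning the abstract and 1.1 with 2.1 is enough for acceptability. It does not remove the mismatch, because the abstract labels the sentence as the primary objective and names the observation periods.

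**A pilot need not rate usual care.** Asking whether a new practice is acceptable and deliverable is a legitimate question by itself. This stands, and rating regular checks is a design choice.

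**Nothing in the documents shows 6-hour gaps on observation nights.** The abstract describes checks every 4 hours. This also stands: the 25% above is only an assumption. It means that the expected contrast is large, but not that the contrast will be shown.

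**A stronger reading is tempting:** that both outcomes are measured only for the intervention, so the comparison cannot be made. The documents do not support it. For feasibility, vitals times are collected on every study day, so a delivery contrast is possible and merely unspecified. For acceptability, the survey items are in Appendix B, whose text is not in the document. The Day +15 questionnaire follows both conditions and could contain comparative items. What can be shown is narrower: no separate acceptability rating is scheduled for an observation period.

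**Conclusion.** The point holds as a mismatch between the stated objective and the plan for it. The abstract and 1.1 word the primary objective as a comparison, while 2.1, 6.1 and 6.3.2 do not make one. As planned, compliance on intervention nights would be reported without the achieved difference in overnight gap, and a null sleep result would be harder to interpret.

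The size of the effect on interpretation cannot be derived from the documents. The 85-point and 60-point figures show only how far the contrast could vary behind one compliance figure. The conclusion rests on two assumptions: that the measures table and 9.2 list every scheduled acceptability rating, and that Appendix B does not already supply a comparison.

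This is a modest improvement, not a condition for the trial to proceed. The primary analysis is descriptive, and no test, threshold or safety rule depends on the comparator. A reader might infer that the primary objective is unanswerable. It is not: as worded in 2.1 it is answered by the planned measures.

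**What to change.** 1. **Feasibility (6.1 and 6.3.2).** Define one overnight-gap summary and apply it in the same way to observation and intervention nights: for example, the longest overnight interval between checks and the share of nights with a gap of at least 6 hours. Report the within-child difference. Use all nights for the main contrast, and show eligible intervention nights separately. Also give the results by 5-day period, so that days +5 to +14, where the order is randomised, can be seen apart from the first observation period. Cost: a few sentences and some programming, since the vitals times are already abstracted under 5.1.1.

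2. **Acceptability (abstract and 1.1).** Remove the comparator so that the wording agrees with 2.1. Cost: wording only.

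3. **Optional.** A few items rating regular checks could be added to the Day +5 packet. Randomization is at the same visit (4.2.3), so they should be completed before allocation is disclosed. The Day +5 to Day +15 difference should be reported as confounded with time since transplant, because 3.1.3 places peak symptom burden typically at day +10. Nurses would still have no comparator. Cost: a small added burden on families, for a comparison that is hard to interpret. Leaving it out is defensible.

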1 BACKGROUND INFORMATION AND RATIONALE

1.1 Introduction

Patients undergoing treatment for cancer face disease, treatment, and environmental obstacles to sufficient, sound sleep¹. Hospitalizations can further worsen sleep quality and quantity due to overnight vitals checks, medication administration, blood draws, and environmental noise and light². For patients undergoing HSCT, the risk of poor sleep is especially high due to protracted hospitalization, frequent vitals checks resulting in multiple night awakenings³, and high symptom burden peaking approximately 10 days post-transplant⁴. Sleep quality and quantity is associated with immune functioning⁵, wound healing⁶, and resistance to infection⁷, all critical to physical recovery from cancer and cancer treatments. Poor sleep may also have a psychosocial impact by limiting engagement in supportive care (PT/OT/School/Creative Arts Therapy/Psychology) due to compensatory daytime sleep and fatigue⁸. Together the physical impact of poor sleep and limited engagement in supportive care may hinder HSCT recovery. Frequent vitals checks are one potential intervention target when seeking to improve sleep. Vitals checks every 4 hours are necessary during conditioning and immediately post-transplant, but for many patients extending the time between vitals checks is possible. Through an aggregated N=1 randomized controlled design (each patient will serve as their own control, with the timing of the 5-day intervention period determined by randomization), the current study will test acceptability, feasibility, and impact on sleep and supportive care engagement of protecting one 6-hour window for nighttime sleep (intervention) relative to regular vitals checks (observation) during HSCT recovery.

1.2 Name and Description of Investigational Product or Intervention

The intervention tested is protecting one 6-hour window for nighttime sleep (intervention) relative to regular vitals checks (observation) during HSCT recovery.

1.3 Relevant Literature and Data

Sleep disturbances are common in pediatric oncology. Sleep disturbances frequently occur across the continuum of cancer treatment into survivorship⁹. Sleep is an understudied area of health-related quality of life¹⁰ (HRQL) that can significantly impact cognitive functioning¹¹, behavior¹², mood¹³, academic progress¹³, and parental and family functioning¹⁴. Sleep quality and quantity is also associated with immune functioning⁵, wound healing⁶, and resistance to infection⁷, all critical to physical recovery from cancer and cancer treatments. Thus, sleep is a logical and important target of assessment and intervention to improve HRQL and health outcomes for individuals—especially children receiving treatment for cancer.

Sleep is central to the experience of cancer-related symptoms. Disrupted sleep can exacerbate the physiological processes of pain¹⁵ and fatigue¹⁶. Psychologically, poor sleep impacts cognitive appraisals of symptoms and symptom-related coping efforts the following day, which may amplify the patient's experience of symptoms¹⁷. Symptoms may then interfere with sleep the following night resulting in a vicious cycle between sleep and symptoms that can be difficult to stop. In pediatric cancer, sleep disturbances are closely related to general symptom burden. Pediatric cancer patients report between 6 (outpatient) and 12 (inpatient) symptoms that co-occur during cancer treatment, with prevalence rates of fatigue, insomnia, pain, and psychological symptoms ranging from 30-50%¹⁸. Studies describing the symptom

cluster of sleep disturbances, fatigue, and pain indicate that fatigue and sleep predict depression and behavior changes in adolescents but not younger patients¹⁹, suggesting a developmental component unique to older pediatric patients in the response to cancer and its treatment. Disturbed sleep may precipitate symptoms or be the result of higher symptom burden, potentially exacerbating symptoms over time.

The hospital environment is extremely disruptive to sleep. Patients undergoing treatment for cancer face disease, treatment, and hospital environmental obstacles to sufficient, sound nighttime sleep¹. Hospitalizations can further worsen sleep quality and quantity due to overnight vitals checks, medication administration, blood draws, and environmental noise and light². For patients undergoing hematopoietic stem cell transplant (HSCT), the risk for poor sleep is especially high due to the protracted hospitalization, frequent vitals checks resulting in multiple night awakenings³, and high symptom burden peaking approximately 10 days post-transplant⁴.

Limited research has examined sleep in pediatric HSCT patients. Sleep, as measured by one global question about sleep quality, worsens from 1-week pre-transplant through 3-weeks post-transplant before improving²⁰. To our knowledge only one study has focused on sleep in pediatric HSCT patients using objective measurement (actigraphy) in 8 children; results indicated patients awaken 12 times per night on average and hospital rooms were entered approximately the same number of times³, suggesting that hospital staff play a role in sleep disruption. In adults, 77% of patients undergoing HSCT report clinically significant poor sleep, and that poor sleep is related to increased fatigue and decreased physical functioning during the hospitalization²¹ while good sleep quality is related to better pre/post HSCT monocytic chemokines, biomarkers indicating immune recovery²². Sleep improves post-transplant; however, at day 100+ 28% of adult patients still report clinically significant sleep disturbances²¹.

Interventions to promote sleep and physical activity have been piloted in pediatric oncology, but they are often not sustainable outside of research. Hospital-based interventions that seek to provide education about sleep and fatigue management²³, encourage physical activity²⁴, and protect 90-minute windows for sleep²⁵ have been tested in small pilot studies in oncology. Generally, families report interventions to be acceptable, but many interventions are not clinically feasible, requiring substantial support to continue outside of the context of research. Scalable interventions that can be integrated into clinical practice are needed to improve the psychosocial health of patients during hospitalizations.

The contribution of staff room entries to poor sleep³ is a logical intervention target. Frequent vitals checks are necessary early in the transplant process but become less necessary post-transplant, thus extending time between vitals checks is likely feasible and has the potential to increase total sleep time. By altering hospital procedures to maximize sleep, we have the opportunity to address hospital-related sleep disruptions and improve outcomes in patients in need of sufficient sleep—patients recovering from HSCT. It is hypothesized that patients who obtain uninterrupted sleep would perhaps participate more in therapies (PT/OT) to regain physical stamina, school activities, creative art therapy, and psychological services to continue cognitive recovery and bolster HRQL. Taken in sum, it is hypothesized that more sleep and increased participation in these activities would ultimately accelerate their recovery and physical functioning.

